1.0 STUDY OBJECTIVE

The primary objective of this clinical study is to prove that a user aided with ClearRead CT InSight is *superior to the unaided reader for detecting actionable lung nodules*.

The secondary objective of this clinical study is to prove that the reader's reading time is not significantly increased when aided with ClearRead CT Insight.

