Retrospective lung CT image series from approximately 300 patients will be included in the study. Approximately one hundred (100) of the patients will have pathology confirmed cancers and approximately two hundred (200) of the patients will be CTs associated with normal patients. Also included as nodule images are those where the actionable nodule was not acted on at that time, but was detected and acted on based on a subsequent CT. These are the prior images where the nodule can be identified and its location is the same as on the “current” image confirmed by the radiologist expert panel (using a majority of three as the decision criterion).

The selected sample, randomly selected from a larger pool of CT cases will be enriched in the following way:

1. Lung nodules (cancers in this study) will be tumor size T1a (20 mm or less). The proportion of nodules 20 mm or less may be increased since this is where we expect the major impact of this software to be.
2. Non-Solid (ground glass) nodules will be added to the sample (based on availability) to determine the performance of the system on non-solid nodules. For this group, to have sufficient cases, we may have to include benign (non-malignant) non-solid nodules.
3. In this project, VIRGINIA TECH will perform a Machine Test of the ClearRead-CT-Insight algorithm followed by a reader performance evaluation study. Riverain will provide a system configured with the operating point set to be used for the reader studies and a configuration for an “open” system to be used for machine testing and FROC generation. Figure 1 shows the reader performance study consists of two arms; **Arm 1**: a baseline read (no secondary content) and **Arm 2**: concurrent, CAD augmented read.

1/12/2015

Riverain Technologies, LLC - Confidential

Figure 1: ClearRead Insight Reader Study Design

1st Arm: Do baseline (measure time, readers score regions according to action and suspiciousness) – mark all locations of concern

2nd Arm: Concurrent read (measure time, readers score regions according to action and suspiciousness) – mark all locations of concern

The primary study hypothesis is that the adjunctive use of ClearRead CT Insight is superior to use of standard lung CT images alone, as measured by the area under the LROC curve.

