3.2 STATISTICAL ANALYSES

Accuracy

To evaluate the hypothesis of superiority in terms of improvement in accuracy for ClearRead CT Insight vs. unaided, a mixed effects model (DBM) will be implemented (similar to the model outlined in Dorfman, Berbaum and Metz, 1997), where variance components will be included to account for reader, case, reader by case, reader by modality, case by modality and reader by case by modality. However, it is anticipated that the three-way interaction will be inestimable and will subsequently be dropped from the statistical model. Specifically, the hypothesis to test for superiority of ClearRead CT Insight vs. unaided is:

$$H_0: AUC_{\text{unaided}} - AUC_{\text{ClearRead CT Insight}} \geq 0.0 \text{ vs. } H_A: AUC_{\text{unaided}} - AUC_{\text{ClearRead CT Insight}} < 0$$

The AUC of the LROC is the primary endpoint to evaluate accuracy and the test of interest will be a two-sided 95% confidence interval on the effect of modality (i.e. *ClearRead CT Insight minus unaided*). Significance will be concluded if the upper bound of the two-sided 95% confidence interval does not include zero. If the null hypothesis (H_0) is rejected, the alternative hypothesis (H_A) is accepted and the superiority of using the ClearRead CT Insight system will be established.

Time

The second co-primary objective is to evaluate reduction in time spent per image for *ClearRead CT Insight vs. unaided*. Specifically, the hypothesis to test for superiority of *ClearRead CT Insight vs. unaided* is:

$$\mathbf{H_0 = T_{unaided} - T_{ClearRead CT Insight} \leq 0 \text{ vs. } \mathbf{H_A = T_{unaided} - T_{ClearRead CT Insight} > 0}$$

To evaluate the hypothesis of non-inferiority in terms of improved read time for *ClearRead CT Insight vs. unaided*, a mixed effects model will be implemented (similar to the model outlined in Dorfman, Berbaum and Metz, 1992), where variance components will be included to account for reader, case, reader by case, reader by modality, case by modality and reader by case by modality. However, it is anticipated that the three-way interaction will be inestimable and will subsequently be dropped from the statistical model.

The read times will be tested using a two-sided 95% confidence interval on the effect of modality (i.e. *ClearRead minus unaided*). Significance will be concluded if the upper bound of the two-sided 95% confidence interval does not include zero.

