3.3 POWER AND SAMPLE SIZE

The power to detect differences in the AUC of the LROC curve for the proposed statistical analysis using the current design baseline, i.e. 300 cases, each corresponding image read by 10 readers, was assessed through a simulation study. Specifically, the model outlined above was used to simulate 500 datasets across a range of effect sizes, where power was defined as the

proportion of datasets that yielded a significant p-value for testing the fixed effect of modality. The method of Dorfman, Berbaum and Metz, 1992 (DBM) was implemented utilizing statistical mixed model theory with jackknife estimates.

These simulations required assumptions regarding the magnitude of the variance components associated with the different random effects. As a pilot study to obtain estimates of variance components was not conducted, variance component estimates from Riverain study SoftView 510(k) (Record # BSSI-PR-09-00006) that uses a similar technology as the proposed ClearRead CT Insight device were used in all power simulations. Please note that the variance components listed in Table V were scaled by the total variance to represent the proportion of total variance explained by each component. All power estimates are dependent upon the appropriateness of the assumed variance components.

Table V: Variance component estimates from previous Softview reader study

Variance Component	Scaled Estimate
Reader (σ_{reader}^2)	0.0003
Case (σ_{case}^2)	0.1258
Modality-by-reader ($\sigma_{mod*reader}^2$)	3.8981E-05
Modality-by-case ($\sigma_{mod*case}^2$)	0.0257
Reader-by-case ($\sigma_{reader*case}^2$)	0.0127
Residual (σ_{res}^2)	0.8355

The mean difference $\Delta\mu = \mu_1 - \mu_2$ between modalities corresponding to a specified effect size γ was then calculated as

$$\Delta\mu = \gamma * \sigma_{res}.$$

Effect sizes of 0, 0.2, 0.5, and 1 representing no effect, a small, a moderate, and a strong effect respectively, were evaluated in this simulation study with the following rationale:

- a) An effect size of 0 was chosen to assess type I error in this study.
- b) An effect size of 0.1 was chosen to correspond to a change in AUC of LROC of 0.084, which is $0.10 \times \sqrt{0.8355}$.
- c) An effect size of 0.2 was chosen to simulate the expected small improvement in accuracy in time.
- d) An effect size of 0.5 was chosen to simulate the expected moderate improvement in accuracy or time.

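### Reading time has two ranks and two aims in the plan, is labelled non-inferiority without a margin, and its only decision rule is stricter than the Section 1.0 objective

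*Combined protocol and SAP*

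**What the plan says.** The statements on reading time in the combined protocol and SAP are these.

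- **Section 1.0:** "The secondary objective of this clinical study is to prove that the reader's reading time is not significantly increased when aided" with the device. No margin is given.
- **Section 2.0:** reading times are listed as an endpoint, with no rank, direction or margin.
- **Section 3.1:** "The primary study hypothesis is that the adjunctive use of ClearRead CT Insight is superior to use of standard lung CT images alone", judged by the area under the LROC curve. Time is not part of it.
- **Section 3.2, Accuracy:** once the AUC null is rejected, "the superiority of using the ClearRead CT Insight system will be established". No condition on time is attached.
- **Section 3.2, Time, first paragraph:** "The second co-primary objective is to evaluate reduction in time spent per image for" ClearRead against unaided. The hypotheses are introduced as superiority: H0, T(unaided) − T(ClearRead) ≤ 0, against HA, > 0.
- **Section 3.2, Time, second paragraph:** the same comparison is introduced with "To evaluate the hypothesis of non-inferiority in terms of improved read time for" ClearRead against unaided. No margin follows.
- **Section 3.2, Time, rule:** a two-sided 95% confidence interval is formed for ClearRead minus unaided. "Significance will be concluded if the upper bound of the two-sided 95% confidence interval does not include zero". The same sentence appears under Accuracy; this point concerns only its use for time.
- **Section 3.3:** the simulation is introduced as "The power to detect differences in the AUC of the LROC curve for the proposed statistical analysis". Item d nevertheless reads "An effect size of 0.5 was chosen to simulate the expected moderate improvement in accuracy or time", and item c also mentions time.

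**The concern.** A reader cannot tell from the plan whether time is secondary or co-primary, or whether the study must show a reduction or only the absence of an increase. Nor is it clear which test delivers the answer. These are different claims. If aided and unaided reads take about the same time, Section 1.0 points to success and Section 3.2 to failure, so one result could be reported either way after the data are seen. Calling time co-primary also raises, without answering, the question of whether both endpoints must succeed.

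**Working it through.** **1. Is there a figure to reproduce?** No. The documents give no power, margin, standard deviation or SE for reading time. The check is therefore a comparison of texts, plus the behaviour of the rule in SE units.

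**2. What does the rule mean?** A single bound cannot include or exclude zero, so the sentence needs interpreting. HA is T(unaided) − T(ClearRead) > 0, which is the same as T(ClearRead) − T(unaided) < 0. The interval is for ClearRead minus unaided. The coherent reading is that the upper bound lies below 0. That is a superiority rule; it is a non-inferiority rule only for a margin of 0, which is superiority again. The bootstrap fallback in Section 3.2 specifies a limit for the AUC difference only, so it supplies no other time rule.

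**3. How do the two readings behave?** Let d be the true difference, ClearRead minus unaided, in SE units. Assume a normal estimate, and assume that a significant increase would be judged by the same two-sided 95% interval (z = 1.96).

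- Section 3.2 rule: P(estimate + 1.96 < 0) = Φ(−1.96 − d).
- Section 1.0 wording taken literally: P(estimate − 1.96 ≤ 0) = Φ(1.96 − d).

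| True difference d | Section 3.2 rule met | No significant increase |
|---|---|---|
| −1 (aided faster) | Φ(−0.96) = 0.169 | Φ(2.96) = 0.998 |
| 0 | Φ(−1.96) = 0.025 | Φ(1.96) = 0.975 |
| +1 (aided slower) | Φ(−2.96) = 0.0015 | Φ(0.96) = 0.83 |
| +2 | Φ(−3.96) < 0.001 | Φ(−0.04) = 0.48 |

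The first reading needs an estimate below −1.96 SE; the second accepts anything up to +1.96 SE. The two cut-offs are 1.96 − (−1.96) = 3.92 SE apart.

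**4. What does co-primary imply?** If both endpoints must succeed, type I error is not inflated, but joint power is also limited by time. If either could carry a claim, and the tests were independent, the chance of at least one false favourable result would be 1 − 0.975² = 0.049. The plan does not say which applies.

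**5. Is power shown for time?** The simulation is described for the AUC. The components in Table V come from an earlier reader study of a similar technology, and none is identified as coming from reading times. Items c and d of Section 3.3 mention time but supply no variance for it.

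**The case against.** The strongest reply is that the rule is conservative: whoever proves a reduction has also proved no increase. That stands, and the plan carries no risk of an easy false claim if the Section 3.2 rule is followed. A second reply is that Section 3.3 speaks of expected improvement, so equal times are not the planning case, and 2.5% is simply the one-directional alpha of any superiority test. That also stands. The 2.5% does not measure harm in this study; it shows how far the two stated aims diverge. A third reply is that Section 3.3 uses standardised effects, which could carry over to time if the variance proportions held. They might, but nothing in the documents supports it.

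A reader might infer three stronger things that the documents do not support.

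- *That the rule does not address the Section 1.0 aim at all.* It does, but more strictly: passing settles the aim, failing leaves it open.
- *That the accuracy claim depends on time.* Section 3.2 rests that claim on the AUC null alone. The word co-primary only makes this unclear.
- *That the zero-effect Superiority rates in Table VI (0.058 to 0.086) show how often the time rule would succeed with equal times.* They concern the AUC. The column also exceeds the Modality Effect column at non-zero effects (0.606 against 0.490, and 0.932 against 0.878). An upper two-sided 95% bound below zero implies two-sided significance, so on the same datasets the rule as written could not succeed more often than a two-sided 5% test. If Modality Effect is such a test, the Superiority column is not the Section 3.2 rule.

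**Conclusion.** The contradiction is in the current text and nothing reconciles it: rank, aim and type of test for reading time each appear in incompatible forms, and non-inferiority has no margin. Confidence in this is high. The consequence is limited to the time claim, which as written cannot be interpreted unless a reduction is shown. Neither reading can show acceptably similar times: the Section 3.2 rule almost never succeeds when they are equal, and the literal Section 1.0 wording is often met despite a real increase. The probabilities rest on a normal approximation in SE units and cannot be turned into seconds from the documents. Power for time is best described as not justified, rather than shown to be inadequate. The sponsor should correct this, but it does not by itself undermine the AUC analysis.

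**What to change.** Before reading data are analysed, make Sections 1.0, 3.1 and 3.2 state one rank, one hypothesis and one rule for time.

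- **Simplest option:** keep the Section 3.2 hypotheses, make time secondary, and delete the co-primary and non-inferiority labels. Revise Section 1.0 to aim at a reduction. Conclude a reduction if the upper bound of the two-sided 95% interval for ClearRead minus unaided is below 0. No margin is needed.
- **If no increase is the real aim:** state a non-inferiority margin in time units, justified by the increase that would be acceptable and not by the SE. Conclude non-inferiority if that upper bound is below the margin.
- **If co-primary status is kept:** revise Sections 1.0 and 3.1 to match, and state whether both endpoints must succeed.

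In every case, replace the wording about a bound not including zero in the time rule with a bound below the stated value. Also remove time from items c and d of Section 3.3, or support it with reading-time variances.

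The first option costs only wording and needs no new data. Its price is that merely equal times would not support a claim of no increase. The non-inferiority option requires a margin to be agreed. Whether 300 cases and 10 readers suffice for time under any option cannot be computed until reading-time variances are available.

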Table VI presents a summary of the power simulations along with additional scenarios with fewer cases with 8 or 10 readers. Superiority is assessed as the proportion of simulations in which the upper bound of the confidence interval on the AUC difference is less than zero. The other power assessment is on the statistical significance of the difference between modality.

Table VI: Power estimates for superiority and statistically significant modality effect using previous Softview reader study to estimate variance components

			Power	
Number of Cases	Number of Readers	Effect Size	Superiority	Modality Effect
300	10	0	0.086	0.082
		0.05	0.606	0.490
		0.1	0.978	0.974
		0.2	1.0	1.0
		0.5	1.0	1.0
270	10	0	0.060	0.060
		0.2	1.0	1.0
		0.5	1.0	1.0
270	8	0	0.058	0.080
		0.1	0.932	0.878
		0.2	1.0	1.0
		0.5	1.0	1.0

The results show that the type I error is approximately controlled at the nominal level, i.e. 0.05, and therefore type I error is maintained at the desired level. Furthermore, the power to detect a change in AUC of at least 10% of the standard deviation is over 80% given the assumed magnitude of the variance components, even with only 270 cases and 8 readers.

Based on data from the literature referenced earlier in this report, potential variability and effect size for sensitivity can be assessed. Based on a mean difference in sensitivity of 0.0914 with overall standard deviation over all estimates of 0.1234 for an effect size of $0.0914/0.1234$, or 0.741, the superiority of ClearRead CT Insight would be detected with adequate power.

There are several scenarios including reduced number of cases and a reduced number of readers. Even with 270 cases and only 8 readers, the power of the study should be sufficient to detect an effect size of 0.1.

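### LROC AUC and reading time each get a full-level test with its own success rule, no rule links the two tests, and the status of reading time is contradictory

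*Combined protocol and SAP*

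**What the plan says.** **Accuracy (Section 3.2).** A directional superiority hypothesis on LROC AUC is tested with a two-sided 95% interval. The rule is: "Significance will be concluded if the upper bound of the two-sided 95% confidence interval does not include zero". If the AUC null is rejected, "the superiority of using the ClearRead CT Insight system will be established". Nothing about reading time is required.

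**Time (Section 3.2).** "The second co-primary objective is to evaluate reduction in time spent per image". The hypotheses are directional, with a shorter aided reading time as the alternative. The next paragraph changes the label: "To evaluate the hypothesis of non-inferiority in terms of improved read time for" the device, with no margin. The test is again at full level: "The read times will be tested using a two-sided 95% confidence interval on the effect of modality". The significance rule repeats the one for AUC and does not refer to the AUC result.

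**Elsewhere.** Section 1.0 makes time the secondary objective, to show that "reading time is not significantly increased when aided with ClearRead CT Insight". Section 3.1 names a single primary hypothesis, on LROC AUC: "The primary study hypothesis is that the adjunctive use of ClearRead CT Insight is superior to use of standard lung CT images alone". Section 2.0 lists the scores and the reading times as numbered endpoints without ranking them. Section 3.3 concludes from its simulations that "therefore type I error is maintained at the desired level".

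No section gives a testing order, a split of alpha, a requirement that both endpoints succeed, a descriptive-only status for time, or an error rate for the two tests together.

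**The concern.** Two confirmatory tests of the same device each carry the full level, and each ends in its own declaration of significance. As written, a study that fails on AUC could still report a significant reduction in reading time at full level. The device's stated primary purpose is better nodule detection, so a confirmed speed benefit after a failed accuracy objective could mislead.

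The conflicting descriptions of time make this harder to settle. Whether the error rate is inflated depends on three things that the plan leaves open or states in two ways: whether time is primary or secondary, whether its hypothesis is superiority or non-inferiority, and whether success needs either endpoint or both.

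**Working it through.** **1. What the plan's own figures cover.** The plan gives no error rate for the pair, so there is none to reproduce. Its type I error statement rests on Table VI. Section 3.3 introduces those simulations as power for the LROC AUC difference. The list of effect sizes mentions time in passing, but each simulation has one outcome, so none can describe two tests together.

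Table VI (300 cases, 10 readers, effect 0.05) does bear on the per-test level. It gives 0.606 for superiority and 0.490 for the modality effect. Using Table V:

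- Difference = 0.05 × √0.8355 = 0.0457.
- SE with every modality term = √[2 × (3.8981E-05/10 + 0.0257/300 + 0.8355/3000)] = 0.0271. Power is 0.516 at one-sided 0.05 and 0.392 at two-sided 0.05, which does not match.
- SE without the modality-by-case term = √[2 × (3.8981E-05/10 + 0.8355/3000)] = 0.0238. Power is 0.610 at one-sided 0.05 and 0.485 at two-sided 0.05, within 2 points of the table. At effect 0.1 the same variant gives 0.986 and 0.970 against the stated 0.978 and 0.974.

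So the superiority column fits one-sided 0.05, whereas a bound of a two-sided 95% interval means 0.025 in one direction. I use 0.025, as Section 3.2 implies, and show 0.05 as a check.

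**2. Either endpoint may support a claim.** Assumptions: both nulls are true, the test statistics are bivariate normal with correlation ρ, each test holds its nominal level, and the AUC bound is read in the direction that favours the device. The documents give no ρ. With a = 0.025 (critical value 1.96),

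P(at least one false claim) = 2a − P(both reject).

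| Assumed ρ | P(both) | P(at least one) | Ratio to 0.025 |
|---|---|---|---|
| −0.5 | 0.0000 | 0.0500 | 2.00 |
| 0 | 0.0006 | 0.0494 | 1.98 |
| 0.3 | 0.0024 | 0.0476 | 1.91 |
| 0.5 | 0.0046 | 0.0454 | 1.82 |
| 0.8 | 0.0110 | 0.0390 | 1.56 |
| 0.9 | 0.0148 | 0.0352 | 1.41 |

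The upper limit is 2 × 0.025 = 0.05. The ratio falls towards 1 as ρ approaches 1.

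**3. Check at one-sided 0.05 per test.** The totals are 0.0975, 0.0878 and 0.0752 at ρ = 0, 0.5 and 0.8, or 1.95, 1.76 and 1.50 times the per-test level.

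**4. Both endpoints must succeed.** A false overall success then requires rejection of at least one true null, so its probability is at most 0.025. There is no inflation.

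**5. AUC first, then time only if AUC succeeds.** If the AUC null is true, any claim requires a false AUC rejection, so the rate is at most 0.025. If the AUC null is false, only the time claim can be false, again at most 0.025. For comparison, an equal split of 0.0125 per test gives 1 − (1 − 0.0125)² = 0.0248 if independent, but it lowers the level of the AUC test.

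**The case against.** The strongest reply is that an either-endpoint design is inferred, not stated. Co-primary can mean that both endpoints must succeed. The sentence on established superiority closes the Accuracy subsection and may be only the conclusion for that hypothesis. A significance rule for each hypothesis is needed under any scheme. Sections 1.0 and 3.1 put AUC first, so a failed AUC test is a failed primary objective whatever time shows. Section 1.0 aims only at no significant increase in time, and Section 3.2 itself uses the word non-inferiority.

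Much of this stands. The plan has no trial-level success rule, so the inflation is conditional. It does not remove the gap. Ranking objectives by importance does not withhold a time claim when AUC fails. The non-inferiority label has no margin, while the stated alternative is a reduction and the interval is compared with zero, so the test as written is one of superiority.

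Two stronger readings are tempting:

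- *The plan runs at about twice its error rate.* A ratio of 1.8 to 2 needs the either-endpoint rule and a correlation of no more than about 0.5. The documents establish neither.
- *The pair exceeds 5%.* At 0.025 per test the total cannot exceed 0.05, the only nominal level the plan states. The excess is relative to the directional level of each test. A total above 0.05 needs a larger per-test level, such as the one-sided 0.05 that Table VI suggests but Section 3.2 does not specify.

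**Conclusion.** The concern holds in a conditional form. Section 3.2 contains two full-level tests with separate success rules and nothing that links them, and the plan contradicts itself on the status and the hypothesis of reading time. As written, a full-level time claim after a failed AUC test is allowed.

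If either endpoint can support a claim alone, the chance of at least one false claim in the device's favour is 0.039 to 0.049 for assumed correlations from 0.8 down to 0. That is 1.56 to 1.98 times the 0.025 of each test, with a ceiling of 0.05. If both must succeed, there is no inflation. These figures assume that each test holds its nominal level. The type I error statement in Section 3.3 concerns the AUC test and gives no assurance for the pair.

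This should be corrected before analysis. It does not call for any change to the number of cases or readers.

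**What to change.** In Section 3.2:

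1. Make reading time a secondary objective, in line with Section 1.0, and remove the co-primary label.
2. State one time hypothesis and use it throughout. Remove either the superiority or the non-inferiority wording, and align Section 1.0 with the choice. If non-inferiority is kept, it needs a margin.
3. Add: *LROC AUC is tested first with the two-sided 95% interval; reading time is tested confirmatorily with its two-sided 95% interval only if AUC superiority is shown; otherwise it is reported descriptively.*

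The cost is a short text edit, with no extra cases, readers or data. AUC keeps its full level and loses no power. The probability of any false claim in the device's favour is at most 0.025, provided each test holds its nominal level. The small downside is that no confirmatory time claim is possible if AUC fails. If the sponsor meant that both endpoints must succeed, the added rule would change the success criterion. The plan should then state the both-must-succeed rule instead, which also needs no alpha adjustment.
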